- The aim of this survey study is to evaluate the awareness, knowledge, and adherence of prescribers (HCPs) and patients/carers to the additional risk minimisation measures (aRMMs) for Hemlibra®. A sample size of 40 HCPs and 70 patients were planned to be surveyed in three European geographic regions. As of the 28th of July 2020, 107 HCPs and 46 patients have completed the respective questionnaires, with a majority of respondents coming from Northern and Western Europe. The number of completed patient questionnaires obtained thus far is smaller than planned and their distribution across the surveyed EU countries is not balanced. The PRAC Rapporteur has requested to extend data collection by 3 months. Consequently, the end of data collection date in the protocol has been moved from Q3 2020 to Q4 2020 (end December 2020) and the availability of the final study report has been moved to Q3 2021 (Section 4; 5; 8.1 and 8.4.2).
- The possibility to recruit patients and carers through HCPs who have not completed the HCP Questionnaire has been added to the protocol. As per the initial protocol, HCPs who have completed the HCP Questionnaire were offered to share Patients Questionnaire and Carer Questionnaire with their patients treated with Hemlibra®, or their carers, respectively. During submission of the protocol to ethics committees in some of the participating countries, lead physicians were provided with the protocol and HCP Questionnaire, which has made them ineligible for participation in the study. In fact, prior exposure would cause an information bias due to the pre acknowledgement of a number of facts that we are asking in the survey. Consequently, access to the patients of these physicians was impeded which had an impact on Patient and Carer Questionnaires data collection. In order to compensate for the loss of patients caused by the above, the protocol has been modified to allow HCPs to share the Questionnaires with patients/carers without prior requirement for HCPs to complete the HCP Questionnaire (Section 8.1; 8.1.1; 8.4.1 and 8.5.2).

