 - HCPs can also choose to participate in the survey by phone in the local language. In this case, an appointment for a phone interview will be scheduled with them.
- Screening questions included at the start of the questionnaire include that HCPs must have prescribed Hemlibra® at least once prior to the study and are not employed by Roche or IQVIA
- Once HCPs have passed the screening questions of the questionnaire, they are moved through the questions one question at a time. For the web-based questionnaire, HCPs can only progress to the next question when the previous question was answered, and only wholly completed questionnaires can be

submitted. If a phone interview is requested, the interviewer will complete the online questionnaire with the HCP.

- If the questionnaire is not completed within one week, the HCPs will be sent a reminder by email one week after the link was sent to them
- If the study sample size is not achieved in the country, a second reminder by phone will be conducted 1.5 weeks after the link has been sent.
- If the questionnaire is still not fully completed, a third and final reminder will be sent to the HCPs by email approximately three weeks after the start of the questionnaire.

For each HCP of the sample, the number of contacts and the date and time when he/she completed the online questionnaire will be recorded. An HCP will be considered as unreachable if he/she has been contacted between 3 and 5 times without having received any answer.

The recruitment in each country will be stopped when the target is reached. If the HCP list has been exhausted in any particular country, the recruitment in this country will be prematurely ended and a strategy will be determined to adjust the sample size with associated weighting.

Patients

HCPs that agree to participate in the patient survey will be sent informational material (kits) for distribution to up to 18 of their patients. The kit will include an explanation of the study and a simplified guide for taking the online questionnaire.

A pre-printed random unique number on the kit is registered by the HCP on a tracking web site. Tracking kit numbers allows monitoring of the number of patient questionnaires coming from the same practice. No log would be kept at the physician level which would link the kit number and the patient's identity.

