8.5 STUDY SIZE

8.5.1 Study Size Calculation

The sample size determination is based on the following sample size formula based on the normal approximation to the binomial:

$$n = \frac{P \cdot (1 - P) \cdot (Z_{1-\alpha/2})^2}{e^2},$$

where P is the expected proportion, e is one half the desired width of the confidence interval, and $Z_{1-\alpha/2}$ is the standard normal Z value corresponding to a cumulative probability of $1 - \alpha/2$ (e.g., if $\alpha = .05$ then $Z = 1.96$).

The proportions of interest (p) here are the proportions mentioned under specific objectives above. As p is not known in advance, we consider it to be 50% (maximum uncertainty). Such a hypothesis yields the most conservative, i.e., the largest, sample size. For example, the required sample size would be 43 for precision levels of 15%. [Table 2](#) provides precision of the estimate (width of 95% CI around the estimate) for a range of sample sizes.

Table 2 Precision of the Estimate for a Range of Sample Sizes

Sample Size	Statistical Precision (%)
43	±15
67	±12
80	±11
96	±10

Prescriber (HCP) survey

A target sample size of 40 completed HCP questionnaires is based on statistical and practical considerations. With a sample size around 40, the statistical precision will be approximately ±15%; the precision would increase with larger sample size. It is to be noted that the final survey sample size will depend on HCPs' willingness to participate in the survey. Regardless of the number of respondents, all completed responses received by the cut-off date will be included in the analysis.

Assuming that the response rate could be as low as 10%, at least 400 HCPs will be invited to participate in the survey in order to increase the number of HCPs passing the screening questions and the likelihood that at least 40 HCPs fill out the questionnaire. This estimate is in line with the response rate reported for similar surveys in the literature ([Agyemang et al. 2017](#)).

Patient/Carer survey

A target sample size of 70 patient/carers questionnaires is based on the below practical considerations and assumptions. With a sample size of 70, the statistical precision will be approximately $\pm 12\%$ (see [Table 2](#)).

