8.7.3 Analysis of Response Rate

The response rates will be calculated. In particular, the following different cases will be distinguished:

- *Selected HCPs (S): HCPs who were selected to be contacted from IQVIA OneKey lists: $S = U + RE$*
- *Unreachable HCPs (U): HCPs who were selected to be contacted from IQVIA OneKey lists but were unreachable (e.g., due to invalid contact information)*
- *Reachable HCPs (RE): HCPs who were reachable and received the invitation to participate in the survey: $RE = N + C + P + R + NE$*
- *Non-respondent HCPs (N): HCPs who were reachable but did not respond to the invitation to participate in the survey*
- **HCPs with completed questionnaires (C): HCPs who completed the entire questionnaire**
- *HCPs with partially-answered questionnaires (P): HCPs who partially completed the questionnaire (provided answers to the questionnaire but never completed/submitted it)*
- **HCPs who refused to participate (R): HCPs who explicitly indicated their refusal to participate**
- *Non-eligible HCPs (NE): HCPs who were confirmed to be non-eligible to participate in the survey after reaching out to them (e.g., retired)*

The HCP participation in the survey will be examined *in particular* as follows:

- Complete response rate = $\frac{C}{RE-NE}$
- Partial response rate = $\frac{P}{RE-NE}$
- Response rate = $\frac{C+P}{RE-NE}$
- Refusal rate = $\frac{R}{RE-NE}$

The participation rates will be presented by region and by speciality.

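### Silent HCPs are unreachable under Section 8.4.2 but non-respondents under Section 8.7.3, and the choice can inflate all four participation rates

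*Protocol*

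**What the plan says.** Section 8.4.2, in its account of HCP recruitment, gives a rule for silence: "An HCP will be considered as unreachable if he/she has been contacted between 3 and 5 times without having received any answer".

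Section 8.7.3 sets up the categories for the participation rates. Selected HCPs (S) divide into unreachable (U) and reachable (RE). U is "HCPs who were selected to be contacted from IQVIA OneKey lists but were unreachable (e.g., due to invalid contact information"). RE is "HCPs who were reachable and received the invitation to participate in the survey" and equals N + C + P + R + NE: non-respondents, completers, partial completers, refusers and the non-eligible. Non-respondents (N) are "HCPs who were reachable but did not respond to the invitation to participate in the survey".

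The complete response, partial response, response and refusal rates all have RE−NE as denominator. U is therefore outside every denominator and N is inside.

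On planning, Section 8.5.1 says: "Assuming that the response rate could be as low as 10%, at least 400 HCPs will be invited to participate in the survey". The target is 40 completed questionnaires.

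**The concern.** Take an HCP with a working e-mail address who is invited, is reminded on schedule and never replies. Section 8.4.2 labels this person unreachable. Section 8.7.3 has a class made for this person, the non-respondents. The two labels put the same HCP on opposite sides of the denominator.

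The overlap is not a rare corner case. The reminder schedule in Section 8.4.2 is an invitation, an e-mail after one week, a phone reminder if the country is short of its target, and a final e-mail. That makes three or four contacts, and Section 8.10 allows up to five. A silent HCP who is followed through the whole schedule meets the 8.4.2 rule, so applying it would leave N nearly vacant.

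Two things are at stake. The first is the response rate, which a reader needs in order to judge volunteer bias; Section 8.9 itself suggests that the HCPs most aware of the risks may be the ones who take part. The second is the comparison of respondents with non-respondents in Section 8.7.4, whose comparison group depends on who is called a non-respondent.

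**Working it through.** **Inputs.** From Section 8.5.1: 400 invited, 40 completed, 10% response rate. From Section 8.7.3: S = U + RE, RE = N + C + P + R + NE, denominator RE−NE. Not in the protocol, so assumed: the share *s* of non-completers who never answer, varied from 25% to 90%. The base case also assumes that every silent HCP was contacted at least three times, that P = NE = 0, that no contact details were invalid, and that the other non-completers refused explicitly.

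**The plan's own figure.** 40 / 0.10 = 400 invitations, which reproduces. The planned 10% is a rate among those invited, so it corresponds to keeping silent HCPs in the denominator.

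**Two codings.** Non-completers: 400 − 40 = 360. Silent: 360*s*.

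- Section 8.7.3 (silent in N): C/(RE−NE) = 40/400 = 10.0%.
- Section 8.4.2 (silent in U): C/(RE−NE) = 40/(400 − 360*s*).

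| Silent share of 360 | Silent | Denominator under 8.4.2 | Complete response under 8.4.2 | Factor vs 10% | Refusal rate, 8.7.3 → 8.4.2 |
|---|---|---|---|---|---|
| 25% | 90 | 310 | 12.9% | 1.3 | 67.5% → 87.1% |
| 50% | 180 | 220 | 18.2% | 1.8 | 45.0% → 81.8% |
| 75% | 270 | 130 | 30.8% | 3.1 | 22.5% → 69.2% |
| 80% | 288 | 112 | 35.7% | 3.6 | 18.0% → 64.3% |
| 90% | 324 | 76 | 52.6% | 5.3 | 9.0% → 47.4% |

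The denominator is shared, so all four rates are multiplied by the same factor, 400/(400 − 360*s*). The factor reaches 2 when 200 HCPs are silent (200/360 = 56%) and 3 when about 267 are (267/360 = 74%).

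**Allowing partial completers and non-eligible HCPs.** Assume P = 10 to 20, NE = 40 to 100 and 80% to 90% of the remainder silent.

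- Low end (P = 20, NE = 100, 80%): remainder 400 − 40 − 20 − 100 = 240, silent 192. The rate moves from 40/300 = 13.3% to 40/108 = 37.0%, a factor of 2.8.
- High end (P = 10, NE = 40, 90%): remainder 400 − 40 − 10 − 40 = 310, silent 279. The rate moves from 40/360 = 11.1% to 40/81 = 49.4%, a factor of 4.4.

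**With the completions reported so far.** The Version 3 rationale states: "As of the 28th of July 2020, 107 HCPs and 46 patients have completed the respective questionnaires". The number invited is not given. If it were 400, there would be 293 non-completers and a rate of 107/400 = 26.8% under Section 8.7.3. Under Section 8.4.2 it would be 107/(400 − 219.75) = 59.4% at 75% silent and 107/(400 − 263.7) = 78.5% at 90%, factors of 2.2 and 2.9.

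**A rate that does not depend on the coding.** C/(S−NE) has the same value however silent HCPs are split between U and N, because S contains both. In the planning case it is 40/400 = 10%.

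**The case against.** The best defence is that the two sections do different jobs. The sentence in Section 8.4.2 stands beside the reminder schedule, names none of the rate categories, and can be read as a rule for when to stop contacting someone; Section 8.10 describes moving on to other HCPs after up to five contacts. Section 8.7.3 is the dedicated section, and the Version 3 rationale says that it was updated to match the SAP. On that reading analysts would simply follow Section 8.7.3. Alternatively, its bad-contact example is only an example, so Section 8.4.2 might supply the working test of reachability.

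Neither reading removes the overlap. No text gives precedence, and both sections use the same term. Stretching U to cover silence leaves a defined class with almost no members. Section 8.9 also treats filtered or unread e-mails as a source of non-response bias, which agrees with Section 8.7.3.

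Four stronger inferences are tempting, and the document does not support them:

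- *N is emptied.* Not entirely. It would keep HCPs contacted fewer than three times, for instance where a country's recruitment closed early, and those who gave some answer but neither started nor refused.
- *The only check of selection bias is lost.* Section 8.9 also compares participants with non-participants. A silent HCP stays in that comparison under either label.
- *The response rate will be inflated several-fold.* That depends on the silent share, which is not stated. At 25% silent the planning-case factor is only 1.3.
- *The study's conclusions on awareness, knowledge and adherence change.* They use submitted questionnaires only, so they do not.

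It also stands that Section 8.7.3 distinguishes all the categories. If their counts are reported, a reader could work out C/(S−NE).

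**Conclusion.** The contradiction is real and lies in current text. An HCP with valid contact details who stays silent through the contact schedule belongs to U by one section and to N by the other, and every participation rate depends on which is used. In the planning case, 10% becomes about 18% to 53% if 50% to 90% of the 360 non-completers are silent, a factor of 1.8 to 5.3. A rate coded by Section 8.4.2 would also not be comparable with the 10% planned among those invited.

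The size rests on the assumed silent share and on silent HCPs having had at least three contacts; the direction does not, because moving any HCP from N to U raises all non-zero rates. The respondent/non-respondent comparison in Section 8.7.4 could lose its main comparison group. Because the success proportions and the comparison in Section 8.9 are unaffected, this should be fixed but does not threaten the main results.

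**What to change.** In Section 8.4.2, reword the rule so that an HCP with valid contact details who gives no answer after three to five contacts is coded as a non-respondent (N). Reserve U for failed contact, such as a bounced e-mail or a wrong number. State in Section 8.7.4 that N is included in the respondent/non-respondent comparison. Alongside the four rates, report C/(S−NE) as a lower bound that treats all unreachable HCPs as eligible non-completers.

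The cost is a one-sentence change, a short addition and minor recoding of the contact log. Section 8.4.2 already records the number of contacts per HCP, and Section 8.8.3 has e-mails and calls traced by software. The reported response rate will be lower than under the present 8.4.2 rule.

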8.4.3 Data Collected at Study Completion

Not applicable

8.5 STUDY SIZE

8.5.1 Study Size Calculation

The sample size determination is based on the following sample size formula based on the normal approximation to the binomial:

$$n = \frac{P \cdot (1 - P) \cdot (Z_{1-\alpha/2})^2}{e^2},$$

where P is the expected proportion, e is one half the desired width of the confidence interval, and $Z_{1-\alpha/2}$ is the standard normal Z value corresponding to a cumulative probability of $1 - \alpha/2$ (e.g., if $\alpha = .05$ then $Z = 1.96$).

The proportions of interest (p) here are the proportions mentioned under specific objectives above. As p is not known in advance, we consider it to be 50% (maximum uncertainty). Such a hypothesis yields the most conservative, i.e., the largest, sample size. For example, the required sample size would be 43 for precision levels of 15%. [Table 2](#) provides precision of the estimate (width of 95% CI around the estimate) for a range of sample sizes.

Table 2 Precision of the Estimate for a Range of Sample Sizes

Sample Size	Statistical Precision (%)
43	±15
67	±12
80	±11
96	±10

Prescriber (HCP) survey

A target sample size of 40 completed HCP questionnaires is based on statistical and practical considerations. With a sample size around 40, the statistical precision will be approximately ±15%; the precision would increase with larger sample size. It is to be noted that the final survey sample size will depend on HCPs' willingness to participate in the survey. Regardless of the number of respondents, all completed responses received by the cut-off date will be included in the analysis.

Assuming that the response rate could be as low as 10%, at least 400 HCPs will be invited to participate in the survey in order to increase the number of HCPs passing the screening questions and the likelihood that at least 40 HCPs fill out the questionnaire. This estimate is in line with the response rate reported for similar surveys in the literature ([Agyemang et al. 2017](#)).

Patient/Carer survey

A target sample size of 70 patient/carers questionnaires is based on the below practical considerations and assumptions. With a sample size of 70, the statistical precision will be approximately $\pm 12\%$ (see [Table 2](#)).

Assuming that 15-20% of the targeted 40 HCPs will agree to propose the survey to up to 18 of their patients, a maximum of 144 patients will receive the survey. If approximately 50% of those patients complete the questionnaire, a sample size of 70 patient/carers questionnaires will be reached. HCPs will be reminded to focus efforts on survey distribution to their patients with inhibitors in order to include 25-35 patients with inhibitors or their carers in the target sample size. If a low patient response rate is observed during the course of the study, a second request to HCPs for patient survey distribution will be done if necessary (see [Section 8.4.2](#)).

Although the defined objective is to reach the targeted sample size of 70 completed patient questionnaires, participation is dependent on the HCPs and the patients and their interest in participating in the survey as well as the volume of Hemlibra sold. Every reasonable effort will be made to reach the target patient sample size in this very limited study population.

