8.5.3 Sample Adjustment

Prescriber (HCP) survey

Since the relative weight of each country and each speciality of HCPs, e.g. paediatric haematologist or haematologist, in the final sample may be different from its real proportion, the extrapolation of the raw survey results to the overall target population would not be relevant without adjustment. The survey results will be weighted to reflect the real proportion in order to allow the extension of the survey results to the overall target population. Both unweighted and weighted results will be presented in the report.

A weight variable will be applied to each statistical unit (i.e., the HCPs) during the results calculation in order to correct any over- or under-sampling that may have occurred for a region. This weight variable will indicate how many unit(s) of the population of interest an observation will count in a statistical procedure. Its value will change per geographic region. The weights will be normalised to obtain their sum equal to the sample size.

Patient/Carer survey

Of note, the sample distribution for patients is uncertain, since it depends on sales of Hemlibra®, the level of contribution of HCPs distributing surveys, the number of patients in the practice of participating HCPs, and the response rate of patients. In any case, the sample will be weighted based on the number of patients who received Hemlibra® in each of the represented geographical regions.

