8.9 LIMITATIONS OF THE RESEARCH METHOD

Bias

The potential for selection bias of physicians participating in a survey is an inherent bias/limitation to any study based on volunteer participation. For instance, it is possible that HCPs willing to participate in the study are those with the highest awareness of the risks associated with Hemlibra®. In order to quantify any selection bias, the distribution of each stratification criterion of physicians (country, speciality, and the other available characteristics present in the screening log) will be compared between participants and non-participants.

Additionally, non-response bias may also be introduced into the study if targeted HCPs have activated filters in their mailbox that block spam and unsolicited emails. Having multiple email addresses could also affect responsiveness, especially if the one used for sending the invitation is not the primary address. HCPs who do not check their email frequently might not receive the invitation during the recruitment period. These are among the reasons why the HCPs will also be contacted by phone.

Moreover, online surveys may promote information bias that may result from social desirability, which refers to the tendency of physicians to give socially desirable/expected responses instead of choosing those reflecting their current knowledge or behaviour, e.g. physicians can copy-paste or refer to information gathered online instead of giving their own opinions ([Wyatt 2000](#)).

Social desirability can affect the validity of survey research findings, but the use of pre-populated items in the questionnaire could/tends to reduce this bias ([Nederhof 1985](#)).

Theoretically, the social desirability bias may also arise when the patients are recruited by the same HCP who has participated in the survey. There is also a potential for a HCP who participated in the survey to increase the awareness of his or her patients about the topic covered in the survey. However, due to the anonymity of the survey, the competitive recruitment (the HCP will not be certain if a patient questionnaire will ultimately be considered in the study), and the fact that the results of the patient survey will not be analysed per centre but as separate samples, this limitation is less likely to happen. As a result, we do not consider it necessary to distinguish between HCPs who participate in the survey from those who recruit patients.

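### The ±12% patient precision in section 8.5.1 assumes 70 independent, equally weighted responses, so it is optimistic for a sample planned to come through 6–8 distributing HCPs and weighted by region

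*Protocol*

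**What the plan says.** Section 8.5.1 introduces its method as follows: "The sample size determination is based on the following sample size formula based on the normal approximation to the binomial". The expected proportion is set at its most conservative value: "As p is not known in advance, we consider it to be 50% (maximum uncertainty". For patients and carers the section concludes: "With a sample size of 70, the statistical precision will be approximately" ±12%, with reference to Table 2. The formula has no design-effect term.

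The next paragraph of 8.5.1 describes how the 70 questionnaires will be obtained: "Assuming that 15-20% of the targeted 40 HCPs will agree to propose the survey to up to 18 of their patients". It puts the maximum number of patients reached at 144, which is 8 × 18.

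Section 8.5.3 says that the patient sample will in any case be weighted by the number of Hemlibra patients in each region. Sections 8.7.2 and 8.7.4 make weighting a second step, done if possible after the unweighted results.

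On the practice as a unit, section 8.4.2 says: "Tracking kit numbers allows monitoring of the number of patient questionnaires coming from the same practice". Section 8.9, discussing social desirability, says: "the results of the patient survey will not be analysed per centre but as separate samples". For the analysis, section 8.7.1 provides for 95% confidence intervals where relevant and names no method.

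**The concern.** The precision formula needs independent responses of equal weight. The recruitment scheme in the same section supplies a handful of practices, each contributing many patients.

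The patient endpoints make positive correlation within a practice very likely. Section 8.3 measures patient awareness by receipt and reading of the alert card and guide and by discussion of risks with HCPs. It also lists distributing those materials, and counselling on the card, as the HCP's own tasks. If one HCP does not hand out the materials, that HCP's patients will tend to score low together. Section 8.9 itself accepts that an HCP who took part in the survey might raise the awareness of his or her patients.

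Regional weighting adds a second loss of information when the weights differ. The rationale for version 3 says that the patient questionnaires collected so far are not balanced across countries, so unequal weights are likely.

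At stake is how much 70 questionnaires can say about the patient proportions. A reader who relies on ±12% would credit the survey with more precision than the planned design gives.

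**Working it through.** **Inputs from the protocol**
- n = 70, P = 0.5, Z = 1.96 (8.5.1).
- Distributing HCPs: 0.15 × 40 = 6 to 0.20 × 40 = 8 (8.5.1).
- Completed HCP questionnaires by 28 July 2020: 107 (version 3 rationale).

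**Assumptions not in the documents**
- ICC within practice: 0.05–0.10 as the main range, 0.01 as a low case.
- Weighting effect (1 + squared coefficient of variation of the weights): 1.2 or 1.5.
- Equal numbers of responses per practice. Unequal numbers would increase the loss.

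**Step 1: reproduce the plan's figure.** Half-width = 1.96 × √(0.25/70) = 11.7%, stated as ±12%. Table 2 also reproduces: ±15% needs 43, ±12% needs 67, ±11% needs 80 and ±10% needs 96. At P = 0.6, the patient success threshold, the half-width is 1.96 × √(0.24/70) = 11.5%. The conservative choice of P therefore offsets almost none of the effects below.

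**Step 2: clustering.** With k practices, m = 70/k, DEFF = 1 + (m − 1) × ICC, effective n = 70/DEFF, and half-width = 1.96 × √(0.25 × DEFF/70).

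| Practices k | m | ICC | DEFF | Effective n | Half-width |
|---|---|---|---|---|---|
| 6 | 11.67 | 0.01 | 1.107 | 63.3 | ±12.3% |
| 6 | 11.67 | 0.05 | 1.533 | 45.7 | ±14.5% |
| 6 | 11.67 | 0.10 | 2.067 | 33.9 | ±16.8% |
| 8 | 8.75 | 0.01 | 1.077 | 65.0 | ±12.2% |
| 8 | 8.75 | 0.05 | 1.387 | 50.5 | ±13.8% |
| 8 | 8.75 | 0.10 | 1.775 | 39.4 | ±15.6% |

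**Step 3: more practices.** If 15–20% of the 107 responding HCPs distributed kits, k would be about 0.15 × 107 = 16 to 0.20 × 107 = 21. This is an assumption, since the protocol does not report the number distributing.
- k = 16, m = 4.375: DEFF = 1.169 at ICC 0.05 and 1.338 at ICC 0.10, giving ±12.7% and ±13.5%.
- k = 21, m = 3.33: DEFF = 1.117 and 1.233, giving ±12.4% and ±13.0%.

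**Step 4: weighting.** With no clustering, a weighting effect of 1.2 gives ±12.8% and 1.5 gives ±14.3%. Combining a weighting effect of 1.2 with ICC 0.05, DEFF is 1.387 × 1.2 = 1.665 with 8 practices (±15.1%, effective n 42) and 1.533 × 1.2 = 1.84 with 6 (±15.9%, effective n 38). This step applies to the weighted results only.

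**The case against.** The strongest reply is that nothing shows the analysis will be wrong. Section 8.7.1 fixes no interval method, section 8.7 leaves detail to the SAP, and kit numbers would allow practice to be taken into account. That stands. A reader might infer that the reported confidence intervals will be too narrow, but the documents do not establish it. The sentence in 8.9 about not analysing per centre is part of a discussion of social desirability and says nothing about how variances are computed.

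Second, 6–8 practices is a planning assumption. Version 3 lets HCPs outside the HCP survey distribute the questionnaire (8.1), and 8.4.2 allows a second wave. With 16–21 practices the loss is modest, as Step 3 shows. This also stands, although 8.5.1 still plans on 6–8.

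Third, the ICC and the weighting effect are assumed, and at ICC 0.01 with near-equal weights ±12% survives. That is true, and it is why a range is given here and not a single corrected figure.

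Fourth, success in 8.7.4 is a threshold on the observed proportion, all analyses are descriptive, and 8.9 already warns that intervals could be very wide. A reader might infer that the success conclusion is overstated. It is not affected, because interval width does not enter the decision.

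Two further inferences also fail. The statement "The weights will be normalised to obtain their sum equal to the sample size" stands in the HCP part of 8.5.3, so it does not show that the patient analysis will treat 70 as the amount of information. Nor does the protocol say that every haematologist at a centre will be invited. They form the recruitment population (8.4.1) and are contacted at random (8.4.2) until the target is met or the list runs out. No cluster size is given, so a parallel claim about HCPs clustered by centre is not supported.

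**Conclusion.** The point holds as one about a stated planning figure. The ±12% is correct arithmetic for 70 independent, equally weighted responses, but the protocol's own scheme does not supply such responses.

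Under an assumed ICC of 0.05–0.10, clustering alone gives ±13.8% to ±16.8% with 6–8 practices (effective n about 34–50) and about ±12.4% to ±13.5% with 16–21. At ICC 0.01 with 6–8 practices it is ±12.2% to ±12.3%. Unequal weights would widen the weighted results beyond this, while the unweighted results carry only the clustering.

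The direction of the error is clear for any positive ICC. Its size depends on an ICC, a number of practices and a spread of weights that the protocol does not give. Patient intervals would be too narrow only if the 8.5.1 formula were reused in the analysis.

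**What to change.** 1. In section 8.5.1, restate patient precision on the effective sample size as a range, naming the assumed ICC, the number of distributing practices and the weighting effect. At the least, say that ±12% is the best case under simple random sampling.
2. Carry a practice identifier from the kit-tracking site into the analysis dataset. It need not link to patient identity.
3. Unless the SAP already does so, compute the patient 95% intervals with a design-based method: practice as cluster, regional weights as sampling weights, and a t reference with degrees of freedom from the number of practices, or another small-cluster correction.

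The cost is some wording and one extra variable. The downside is a less favourable stated precision and wider intervals, which will be somewhat unstable if practices are few. With k − 1 degrees of freedom and clustering alone at ICC 0.05–0.10, the half-width is about ±16.6% to ±18.8% with 8 practices and ±19.0% to ±22.1% with 6. A larger number of distributing practices reduces both problems.
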